7.6 Statistical Analysis

The completeness of the data affects the integrity and accuracy of the final study analysis. Therefore, efforts will be made to ensure complete, accurate and timely data collection, and to avoid missing data. The procedures for handling missing, unused, or spurious data, along with the detailed method for analysis of each variable, transformations, and exploratory analyses will be presented in the Statistical Analysis Plan (SAP); the information below is intended as a guide to planned analyses.

The study is designed in 2 parts: dose escalation (Phase 1) followed by dose-expansion (Phase 2). Phase 1 dose escalation is exploratory in nature and inferential statistics are not the primary focus. Data from the dose escalation and dose expansion components will be summarized separately. There is no intention to compare dose cohorts. In Phase 2, all comparisons will be conducted descriptively.

7.6.1 Sample Size Determination

During Phase 1, dose escalation will be based on 3+3 guidelines to determine the RP2D and evaluate safety data (including DLTs and TEAEs) and assess the PK-PD of each dose level. The sample size in Phase 1 is predicated on the number of dosing cohorts examined and the number of observed DLTs.

Two treatment arms will be evaluated in Phase 2: BION-1301 monotherapy and BION-1301+DEX.

In Phase 2, a sample size of 29 evaluable subjects in the BION-1301 monotherapy arm achieves 80% power to detect a difference of 9% in ORR using a one-sided exact test with a target significance level of 0.05. The actual significance level achieved by this test is 0.034. The calculation assumes that the population ORR under the null hypothesis is 1% and under the alternative hypothesis is 10%. The sample size includes subjects treated at the corresponding RP2D/schedule during Phase 1 (Dose Escalation).

If more than one dose/schedule is studied in Phase 2, this design will be applied to each RP2D independently.

In Phase 2, a sample size of 14 evaluable subjects in the BION-1301+DEX arm, achieves 80% power to detect a difference of 19% in ORR using a one-sided exact test with a target significance level of 0.05. The actual significance level achieved by this test is 0.008. The calculation assumes that the population ORR under the null hypothesis is 1% and under the alternative hypothesis is 20%.

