7.1.1 Phase 1: Dose Escalation

Phase 1 of the study seeks to evaluate the safety and tolerability of BION-1301 when administered as a single agent. Initially, BION-1301 will be administered at the 50 mg dose level; subsequent dose escalations will follow both safety and pre-specified dose escalation rules (Section 7.1.1.1).

Subjects within a dose cohort will be evaluated through Cycle 1 for DLTs (28-day evaluation period) and PK-PD parameters (14-day evaluation period). Dose escalation decisions will be based on available safety, PK-PD, and efficacy data from all evaluable subjects in each cohort.

The Safety Review Team (SRT) convened for the study, will consist of the Investigators who enrolled subjects in the study, Medical Monitor, and Sponsor representatives. Dose escalation and reduction decisions, additional enrollment specifications, and recommendation of the RP2D(s) and dosing schedule for expansion will be made by the SRT. TEAEs, DLTs and safety data will continue to be reviewed by the SRT throughout the study.

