7.1.1.1.2 Definitions for Dose Escalation and Identification of Recommended Phase 2 Dose

Target Engagement (TE) is defined as the reduction of free APRIL in blood relative to baseline. In this study, TE will be measured by the levels of free APRIL in the serum at trough, relative to study baseline. TE will be typically quantified on the basis of PK-PD modeling and simulation.

Full TE is defined as complete APRIL antagonism (i.e. >95%) in the blood at trough, as measured by the level of remaining free APRIL in serum. Full TE corresponds to levels of free APRIL of $\leq 5\%$ relative to baseline for the duration of the dosing cycle at steady state.

Mark TE is defined as complete APRIL antagonism (i.e. >95%) in bone marrow, as measured by the level of remaining free APRIL in bone marrow. Mark TE corresponds to levels of free APRIL of $\leq 5\%$. TE in bone marrow will be calculated using PK-PD modeling of available clinical data.

Maximum-tolerated Dose (MTD) is defined as the maximum dose at which an acceptable level of toxicity is observed, as evidenced by a DLT rate of < 33% (i.e. 0 DLT in 3 evaluable subjects or ≤ 1 DLT in 6 evaluable subjects). The MTD is one dose level lower than a dose level where a DLT rate $\geq 33\%$ was observed.

Recommended Phase 2 Dose is defined as the dose level at or below the MTD (or up to the highest dose tested if MTD is not reached) selected on the basis of a cumulative review of safety, tolerability, and clinical activity; may include PK, PD, and other available efficacy data.

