7.4.1 Method of Assigning Subjects to Treatment

All subjects will be sequentially assigned a unique identification number during Screening.

Subjects meeting all inclusion and exclusion criteria and completing all screening requirements will be assigned treatment depending on the study enrollment status:

- In Phase 1 of the study, subjects will be sequentially assigned to dose cohorts as specified in the study design ([Section 7.1.1](#)).
- In Phase 2 of the study, subjects will be randomized 1:1 ratio to either the BION-1301 or BION-1301+DEX treatment arm until the BION-1301+DEX arm is filled (n=14); thereafter, all remaining subjects will be assigned to BION-1301 until the arm is filled (n=29 total at selected dose/schedule). If more than one dose level/schedule of BION-1301 is selected for further evaluation in Phase 2, subjects will be randomized in the same fashion.

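### The 0.034 significance level stated for the 29-subject ORR test is nominal, because the 29 include Phase 1 subjects whose responses may help choose the RP2D

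*Protocol*

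**What the plan says.** Protocol section 7.6.1 states that "a sample size of 29 evaluable subjects in the BION-1301 monotherapy arm achieves 80% power to detect a difference of 9% in ORR". The test is exact and one-sided, aimed at the 0.05 level. The null ORR is 1% and the alternative 10%. It continues: "The actual significance level achieved by this test is 0.034". The same paragraph then counts earlier subjects: "The sample size includes subjects treated at the corresponding RP2D/schedule during Phase 1 (Dose Escalation"). The Synopsis repeats all of this, and section 7.4.1 confirms that 29 is the pooled figure ("n=29 total at selected dose/schedule").

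On how the dose is chosen, section 7.1.1.1.2 defines the RP2D as a dose level at or below the MTD "selected on the basis of a cumulative review of safety, tolerability, and clinical activity", and allows PK, PD and other efficacy data as well. Section 7.1.1 adds: "Dose escalation decisions will be based on available safety, PK-PD, and efficacy data from all evaluable subjects in each cohort".

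Two other places bear on the point. The opening of section 7.6 says that escalation and expansion data are summarized separately and that Phase 2 comparisons are descriptive. Section 7.6.5.1 makes ORR the primary efficacy analysis, reported with a 95% Clopper-Pearson interval. Neither adjusts for the reuse of Phase 1 subjects.

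**The concern.** A binomial tail for 29 subjects is the level of the test when all 29 are a sample fixed without regard to outcome. Here 3 to 6 of them may come from a cohort that was picked after its responses were seen. A cohort with a chance responder is then more likely to be the one carried forward, and that responder is counted again.

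The design is sensitive to this because the bar is low. The rule implied by the stated level and power is 2 responses in 29, so one Phase 1 responder supplies half of what is needed. At a 1% ORR a given cohort of 3 has a 3.0% chance of containing a responder, while the best of six such cohorts has a 16.5% chance (1 − 0.99^18). At stake are an understated false-positive risk and an upward bias in the pooled ORR, which also shifts its Clopper-Pearson interval.

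**Working it through.** **Inputs from the documents.** n = 29, null 1%, alternative 10%, target one-sided 0.05, stated level 0.034 (Protocol 7.6.1); pooled total 29 (7.4.1); at least 3 evaluable subjects and up to 6 per cohort (7.1.1.1); 21 subjects in 6 cohorts (SAP 3.1).

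**Assumptions not in the documents.** A 1% ORR at every dose under the null; the number of cohorts open to selection; the weight given to response; the split of the 21 subjects over the 6 cohorts.

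**Step 1: reproduce the plan's figure.** With X ~ Binomial(29, p):

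- p = 0.01: P(X ≥ 2) = 1 − 0.99^29 − 29 × 0.01 × 0.99^28 = 1 − 0.7472 − 0.2189 = 0.0340.
- p = 0.10: P(X ≥ 2) = 1 − 0.0471 − 0.1518 = 0.801.
- A cut-off of 1 response would give a level of 0.253, so the implied rule is at least 2 responses.

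Both stated figures are right for a fixed sample.

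**Step 2: level under full selection on response.** Take K cohorts of m subjects, carry forward the one with the most responses, and add 29 − m new subjects. Let F be the Binomial(m, 0.01) distribution function and M the largest count, so P(M = x) = F(x)^K − F(x − 1)^K. With Y ~ Binomial(29 − m, 0.01),

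level = P(M = 0)·P(Y ≥ 2) + P(M = 1)·P(Y ≥ 1) + P(M ≥ 2).

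Example with K = 3, m = 6: 0.8345 × 0.0220 + 0.1611 × 0.2064 + 0.0044 = 0.0184 + 0.0333 + 0.0044 = 0.056. With K = 1 the formula returns 0.0340, so the excess comes from selection alone.

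| Candidate cohorts K | 3 per cohort | 6 per cohort |
|---|---|---|
| 1 | 0.034 | 0.034 |
| 2 | 0.040 | 0.045 |
| 3 | 0.046 | 0.056 |
| 4 | 0.052 | 0.066 |
| 6 | 0.063 | 0.085 (36 subjects) |

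**Step 3: cohorts that add up to the 21 subjects reported.** The split is not given, so two were enumerated exactly, with ties in response count resolved in different ways.

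| Assumed sizes | Ties to largest cohort | Ties at random | Ties to smallest cohort |
|---|---|---|---|
| 3, 3, 3, 3, 3, 6 | 0.0625 | 0.0665 | 0.0673 |
| 4, 4, 4, 3, 3, 3 | 0.0658 | 0.0666 | 0.0675 |

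Full selection therefore gives about 0.063 to 0.067. The expected pooled ORR at a true 1% becomes about 1.5% to 1.6%.

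**Step 4: partial weight.** If response decides the choice half the time, the level is the average of 0.0340 and the full-selection value. For the 21-subject splits this is (0.0340 + 0.0625)/2 = 0.048 to (0.0340 + 0.0675)/2 = 0.051. For two or three candidate cohorts it is 0.037 to 0.045.

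**Step 5: testing only new subjects, rule of at least 2 responses.**

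| New subjects | Level | Power at 10% |
|---|---|---|
| 23 | 0.022 | 68% |
| 26 | 0.028 | 75% |
| 29 | 0.034 | 80% |

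**The case against.** The strongest reply is that no ORR hypothesis test is part of the planned analysis. Section 7.6.5.1 plans an estimate with an interval, section 7.6 describes itself as a guide and calls Phase 2 comparisons descriptive, and the exact test appears only as the reason for 29. The pooling is disclosed openly, and 0.034 is correct for the test it describes. This limits the consequence. It does not make 0.034 the level of the design described in the same paragraph, and the estimate and interval that are planned carry the same selection.

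A second reply is that response would rarely drive the choice. Target engagement and PK-PD are central to escalation, safety and tolerability also enter the RP2D definition, and the lowest doses may not be realistic candidates. This stands as an argument about size: with two or three candidate cohorts and half weight, the level stays within the 0.05 target.

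A third is that separate summaries of escalation and expansion (section 7.6) already supply an expansion-only ORR. That is a possible reading, but it sits beside a pooled 29, and nothing says which ORR is primary.

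Some stronger inferences go beyond the documents. A reader might conclude that the level does exceed 0.05, or reaches 0.085; the latter needs six cohorts of 6, or 36 subjects, against 21 reported, and full selection on response. A reader might also conclude that a go decision could rest on one Phase 1 response plus one later response; no section states a go rule, and the cut-off of 2 is inferred from the stated level and power.

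**Conclusion.** The point holds as a correction to a stated design figure. The 0.034 is nominal: it is exact only if the RP2D is chosen without regard to response, and the protocol says that clinical activity is part of the choice. Under a 1% ORR at every dose and a rule of at least 2 responses, the range is 0.034 with no selection on response, about 0.05 with half weight and six cohorts totalling 21 subjects, and about 0.063–0.067 with full selection over those cohorts. It is at most about 0.056 with two or three candidate cohorts. So the level can pass 0.05 but need not, and the documents do not fix the weight on response that would settle it. The pooled ORR and its Clopper-Pearson interval are biased upward to the same extent.

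The BION-1301+DEX arm has no stated Phase 1 carry-over and is not affected. Nor are the reported results: SAP sections 3.6 and 10 record that Phase 2 was not enrolled and that its analyses are omitted.

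**What to change.** Keep the pooled 29. In the Synopsis and section 7.6.1, replace the statement of an actual level of 0.034 with wording such as: nominal significance level 0.034, assuming the RP2D is chosen independently of response; up to about 0.07 if it is chosen on Phase 1 response. In section 7.6.5.1, state that the ORR with its Clopper-Pearson interval in subjects enrolled after RP2D selection is reported beside the pooled ORR. This also reconciles the pooling with the separate summaries promised at the start of section 7.6.

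The cost is one extra row in any Phase 2 ORR table and a less favourable stated figure. Confining the test to new subjects would remove the problem, but it is a trade-off: within a total of 29, power falls to 75% (26 new) or 68% (23 new), and restoring 80% takes 29 new subjects, which is 3 to 6 more per RP2D. The current SAP needs no change, because it covers Phase 1 only.

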7.6.2 General Considerations

Descriptive statistics will be provided for selected demographic, safety, and PK data by dose level. Descriptive summaries on continuous data will include number of subjects, means, medians, standard deviations, minimum and maximum values. Categorical data will be summarized using frequency counts and percentages. Descriptive summaries of time to event data from Kaplan Meier estimates will include the number of events, number censored, medians, quartiles and 95% confidence intervals (CIs). Graphical summaries of the data may be presented. All data will be listed for all treated subjects.

If more than 1 dose level or dosing schedule is evaluated in Phase 2, there are no formal comparisons planned between the RP2Ds. No inferential comparison between BION-1301 and BION-1301+DEX arms will be performed in Phase 2.

All statistical analyses will be performed using SAS.

7.6.3 Analysis Sets

The following analysis sets will be used for this study:

- ***Evaluable Analysis Set (EAS)***: All subjects who received any amount of study drug and have at least one evaluable post-baseline tumor response assessment or were discontinued due to toxicity. The EAS will be the primary population for analyses of ORR, PFS, DCR, DOR, and relative reduction in M-protein.
- ***Full analysis set (FAS)***: All subjects who receive any amount of study drug. The FAS will be used for analyses of OS, biomarkers, sensitivity analysis of select tumor response-related endpoints, and exploratory endpoints.
- ***Safety population***, defined as all subjects who receive any amount of study drug. All safety analyses will be based on this population. The safety population and FAS are identical.

All analyses of safety, PK, PD, and efficacy data will be performed on all subjects who were enrolled and received at least one dose of study drug.

Additional analysis sets (e.g. evaluable per protocol analysis set) may be defined in the SAP.

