7.6.5.1 Efficacy Variables and Analysis (Phase 2)

Objective Response Rate (ORR) defined as the proportion of subjects with a best overall response of sCR, CR, VGPR, or PR, according to IMWG criteria ([Appendix A](#)) as assessed by the Investigator, will be used as the primary analysis for efficacy. The ORR along with a 95% CI, based on the Clopper-Pearson interval will be reported. Secondary analyses of ORR may be repeated in FAS, counting a missing best overall response as a non-responder. ORR will be summarized by each response assessment and best overall response.

Relative reduction in M-protein is defined as the maximum percent reduction from baseline in serum and urine M-protein levels at any time point while on treatment.

Progression-free survival (PFS) is defined as the time from first dose of study drug to first documentation of disease progression or death due to any cause. Subjects who do not experience PD and are alive will be censored at the time of last evaluable tumor assessment. Subjects who do not experience PD and start new anti-cancer therapy will be censored at the last evaluable tumor assessment on or prior to the time of the new anti-cancer therapy. For analyses conducted in the FAS, subjects with no evaluable post-baseline tumor assessments will be censored at the time of receipt of first study drug. Subjects who are lost to follow-up for assessment of PD will be censored at their last evaluable tumor assessment.

Overall Survival (OS) defined as the time from first dose of study drug until date of death due to any cause. Subjects without documentation of death at the time of analysis will be censored as of the date the subject was last known to be alive, or the data cut-off date, whichever is earlier.

PFS and OS will be summarized using Kaplan-Meier estimates.

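### The primary Phase 2 efficacy set omits treated subjects lost before an evaluable response assessment, which inflates ORR and DCR (and PFS where early events are lost) and conflicts with the all-treated statement in the same section

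*Protocol*

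**What the plan says.** Protocol 7.6.3 defines the EAS as "All subjects who received any amount of study drug and have at least one evaluable post-baseline tumor response assessment or were discontinued due to toxicity". It then gives that set its role: "The EAS will be the primary population for analyses of ORR, PFS, DCR, DOR, and relative reduction in M-protein". The FAS, which is everyone who received any study drug, has a supporting role: "The FAS will be used for analyses of OS, biomarkers, sensitivity analysis of select tumor response-related endpoints, and exploratory endpoints".

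Further down, the same section says: "All analyses of safety, PK, PD, and efficacy data will be performed on all subjects who were enrolled and received at least one dose". That describes the FAS, not the EAS.

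Protocol 7.6.5.1 offers the all-treated ORR only as an option: "Secondary analyses of ORR may be repeated in FAS, counting a missing best overall response as a non-responder". It defines PFS as "time from first dose of study drug to first documentation of disease progression or death due to any cause", but says that in FAS analyses a subject with no evaluable post-baseline assessment is censored at first dose. No exception is stated for death. Section 7.6.5.2 analyses DCR in the same way as ORR.

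The abbreviated SAP covers Phase 1 only. Its section 6.1 reports on all treated subjects, and its section 10 omits the Phase 2 efficacy analyses.

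**The concern.** Membership of the primary set depends on what happens after treatment starts, and the rule is uneven. A subject with no assessment who stops for toxicity is kept. A subject with no assessment who dies of myeloma, deteriorates or withdraws is dropped. The first scheduled serum and urine assessment after Cycle 1 Day 1 is on Cycle 2 Day 1, about four weeks later (Table 2-1). The population has had at least three prior regimens and has no established option left (7.3), so some early loss is plausible.

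Section 7.6.1 sizes each arm against a fixed 1% null, so no control arm absorbs the bias. The two statements in 7.6.3 also allow two analysts to produce different primary ORRs, both following the protocol. The conservative version is optional, and missing-as-non-response is stated only for that version. How the EAS counts a toxicity discontinuation with no assessment is therefore not specified.

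**Working it through.** **Inputs.** From 7.6.1: monotherapy n = 29 evaluable, null 1%, alternative 10%, stated alpha 0.034, power 80%. BION-1301+DEX n = 14 evaluable, null 1%, alternative 20%, stated alpha 0.008, power 80%. Not in the documents, so assumed: d, the share of treated subjects outside the EAS (10-20%), and q, the share with a PFS event before any evaluable assessment (5-20%).

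**Step 1: reproduce the plan.** With success at 2 or more responders, P(X ≥ 2) = 1 - (1-p)^n - n·p·(1-p)^(n-1).
- n = 29: alpha at p = 0.01 is 0.0340; power at p = 0.10 is 0.801.
- n = 14: alpha at p = 0.01 is 0.0084; power at p = 0.20 is 0.802.

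Both designs reproduce.

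**Step 2: ORR and DCR.** Excluded subjects contribute no responders, so rate in EAS = rate in all treated / (1-d).
- d = 10%: 0.10/0.90 = 11.1%.
- d = 20%: 0.10/0.80 = 12.5%.

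DCR carries the same factor, because a subject with no assessment cannot be shown to have stable disease either.

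In counts, 3/29 in the EAS is 10.3% (95% CI 2.2-27.4%). With 3 further treated subjects excluded, the all-treated figure is 3/32 = 9.4% (2.0-25.0%). With 6 excluded it is 3/35 = 8.6% (1.8-23.1%).

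**Step 3: type I error, if enrolment continues until 29 subjects are evaluable.** A true all-treated ORR of 1% becomes 0.01/(1-d) inside the EAS.

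| d | ORR in EAS under the null | alpha, n = 29 | alpha, n = 14 |
|---|---|---|---|
| 0 | 1.00% | 0.034 | 0.008 |
| 10% | 1.11% | 0.041 | 0.010 |
| 20% | 1.25% | 0.051 | 0.013 |

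The monotherapy arm passes its 0.05 target at about d = 20%. The DEX arm stays well inside it.

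**Step 4: PFS.** After the early window, S_all(t) = (1-q)·S_EAS(t). If EAS survival is exponential with median m, the all-treated median is m·log2[2(1-q)]. For an assumed m of 3.0 months:
- q = 5%: 2.78 months.
- q = 10%: 2.54 months.
- q = 20%: 2.03 months.

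If instead nobody in the EAS has an event before month 0.92, the median is 0.92 + 2.08·log2[2(1-q)], which gives 2.68 months at q = 10% and 2.33 at q = 20%. Only subjects with an early event count towards q. Someone who withdraws event-free before any assessment would be censored at time zero, so leaving that subject out does not move the Kaplan-Meier curve.

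**Step 5: would the FAS alone repair PFS?** Taken literally, the 7.6.5.1 rule censors every FAS subject without a post-baseline assessment at first dose, including those who died. Censoring at time zero adds nothing to the curve, so these early events would stay lost after a change of set.

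**The case against.** The strongest reply is that the excluded group may be small. Section 7.5.2.2.1 asks for a prompt serum assessment when progression is suspected. Sections 7.5 and 7.5.2.2 continue response assessments after treatment stops for reasons other than progression. Table 2-1 has an end-of-treatment assessment, entry requires ECOG 0-1, and toxicity discontinuations are retained. All of this stands, and it is why the sizes above are conditional on assumed values of d and q. It limits the bias but does not change its direction or resolve the contradiction.

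It is also fair that 7.6.5.1 already describes an all-treated ORR with missing counted as non-response. What remains is that it is optional and secondary. The exact test appears only in the sample-size section. ORR is to be reported with a Clopper-Pearson interval and Phase 2 comparisons are descriptive (7.6), so the alpha figures describe the design calculation, not a planned declaration of success.

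A reader might infer a loss of power, because 7.4.1 randomizes "until the BION-1301+DEX arm is filled (n=14") and fills monotherapy at 29. The documents do not support this. Section 7.6.1 sizes the arms in evaluable subjects, and 7.4.1 can be read as the same counts. If the arms did close at 29 and 14 treated, excluded subjects could not have been responders. The number of responders would be the same in either set, and with the cutoff at 2, power at fixed all-treated rates would stay at about 80% and monotherapy alpha at about 0.034. The inflated alpha in step 3 belongs only to the case where 29 evaluable subjects are reached.

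**Conclusion.** The point holds for the protocol's Phase 2 plan. Section 7.6.3 contradicts itself on the efficacy population, and the set it names as primary favours the drug. ORR and DCR are inflated by 1/(1-d): 11-25% in relative terms for an assumed d of 10-20%. The monotherapy alpha reaches 0.041-0.051 if 29 evaluable subjects are accrued. If there are no responders, ORR is zero in either set.

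PFS is overstated only to the extent that early deaths or progressions are excluded. Its size rests on the assumed q, the assumed 3-month median and the exponential form. DOR is confined to responders and is not affected.

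A reader might also infer that the trial's reported results are biased. They are not on this account: SAP 3.6 records that Phase 2 was not enrolled, and the SAP drops these analyses and reports on all treated subjects.

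**What to change.** In 7.6.3:
- Make the FAS the primary set for ORR, DCR and PFS.
- Require a missing best response to count as non-response for ORR and as no disease control for DCR, in place of the optional wording in 7.6.5.1.
- Keep the EAS as a sensitivity analysis.
- Align the later all-analyses sentence with these choices.

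In 7.6.5.1, amend the FAS censoring rule so that a death or documented progression before the first evaluable assessment counts as a PFS event on its date. Only event-free subjects with no assessment are then censored at first dose. Without this second change, moving PFS to the FAS has no effect on the early events.

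The cost is wording, plus a slightly less favourable ORR, DCR and PFS. No extra data collection is needed, since deaths are already recorded on the case report form (7.5.2.3). As Phase 2 did not open, the change matters only if this protocol text is reused.
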